The potential utility of ECochG during CI is illustrated by the following scenario: if the CI electrode touches the delicate structures of the cochlea (i.e., the basilar membrane or the spiral ligament) during insertion, the ECochG potentials become smaller in amplitude. With a real-time measurement system used during electrode insertion, decrease in ECochG potentials could be detected, and the surgeon could more purposely employ their modifications to insertion technique such as changing the insertion angle to avoid trauma or translocation.

Use of intra-cochlear electrodes for ECochG offers an additional capability of observing potentials post-operatively in the clinic. ECochG allows an objective method of monitoring hearing at regular intervals over the early post-operative period and may give insights into hearing outcomes.

Study Design

A prospective, randomized, multi-center controlled study design will be used in this study. The total study duration will be up to two years. This study will be conducted in agreement with the Internal Review Board (IRB). The study will be registered through Clinical Trials.gov (account created; registration pending IRB approval).

Outcome Measures

The post-operative outcome measures of this study will be (1) the CI electrode's scalar position as indicated by post-operative computed tomography (CT) and (2) post-operative hearing performance. Following the clinical convention, the surgeon will pre-operatively select the type of CI electrode (i.e., the MidScala electrode or the SlimJ electrode) that they would like to use during surgery. As detailed below, the patient will then be randomized to "audible ECochG signal off" or "audible ECochG signal on."

Hypotheses

The hypotheses of this study are that:

- (1) Changes in the ECochG signal observed during CI electrode insertion will correlate with insertion position outcomes as indicated by post-operative CT scan.
- (2) Participants randomized to "ECochG audible response on" will demonstrate a significantly lower rate of scalar dislocation compared to participants randomized to "ECochG audible response off."
- (3) Changes in the ECochG signal during CI electrode insertion will correlate with post-operative audiogram.
- (4) Post-operatively, changes in the ECochG *signal over time in clinic* will correlate with changes observed *over time* in post-operative audiograms.

Participants

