This condition is identical to the current standard-of-care for conventional CI surgery used worldwide. The surgeon will perform his or her electrode insertion without ECochG monitoring. Minute manipulations of the electrode are a normal part of conventional electrode insertion; manipulations such as redirecting the insertion vector or slowing down insertion speed will be made, as deemed necessary by the surgeon. A full electrode insertion will be performed, as appropriate. The ECochG responses will be recorded, but the surgeon will be blinded to this information during surgery.

Arm 2: Audible ECochG Response On

This condition will have the audible ECochG response on and available to the surgeon. In this condition, the surgeon perform a conventional electrode insertion while listening to the running ECochG signal for drop in amplitude (suggesting impending trauma). If no drop is detected, insertion will proceed to the full electrode length according to the standard-of-care. If an ECochG amplitude drop is observed, the surgeon will place this observation in its clinical context and evaluate insertion parameters, (i.e., insertion vector, insertion speed, etc.), customary practice with conventional CI surgery, but here

supplemented by the ECochG response. In the case of an ECochG amplitude drop that does not recover, the standard-of-care practice of achieving a full electrode insertion will be followed.

Protocol timeline

1) Pre-Operative (typically 1-30 days before surgery)

- a) Standard counselling regarding CI study; collect consent form for adults or assent form for pediatric participants; collect data release forms.
- b) The surgeon makes his or her CI electrode selection between two options: (1) the HiFocus SlimJ (lateral wall array) or (2) the HiFocus MidScala. Electrode selection is a normal component of conventional CI surgery. All CIs models to be utilized in this study are FDA-approved and will be used within their approved indications (Ultra MS: Model# CI-1600-04, FDA PMA Approval Number P960058/S117; Ultra Slim J: Model# CI-1600-05, FDA PMA Approval Number P960058/S121).
- c) Pure tone audiometry (standard-of-care pre-operative CI candidacy evaluation). In pediatric patients, for whom completion of pure tone audiometry may be difficult or unreliable, auditory brainstem response (ABR) testing can be used to supplement or estimate behavioural thresholds.
- d) Pre-operative CT scan (standard-of-care) for surgical planning.

2) Day of surgery

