The implant, sound processor, and the clinical programming interface (CPI) hardware are all FDA-approved, and their use in the study is not associated with any additional risk to the patient. ECochG devices are FDA-cleared Class II devices. For an example of an FDA 510(k) clearance letter for the Otometrics device (k143670), please see Appendix. The ECochG recording software is not FDA/*Conformité Européenne* (CE) certified, but it has been thoroughly tested per AB's internal quality system. The recording software is not part of the CI operation and does not introduce any new or changed risk to the patient. It has been verified that the experimental software does not affect the performance of the FDA-approved software or hardware. Further, the entire protocol detailed above has been utilized and reported upon across several institutions validating the feasibility, ease, and safety of this modification to the convention "no feedback" approach to CI electrode insertion. This study's principal investigator (PI) also has experience using the current system.

Data Acquisition and Storage

Post-operative audiometric measurements and post-operative CT scan results will be recorded in the participant's study binder. Results of intra-operative and post-operative ECochG will be saved by the ECochG software program but will also be printed and kept in the participant's binder. All files will be archived. The main study results will be transferred to Excel-files for analysis. Further analyses will be done with Excel, Matlab or statistical software packages. A member of the Biostatistics Department will assist in statistical analysis. All results will be made anonymous prior to being shown to any third party. It will not be possible for any individual study participant to be recognized from his or her study data.

In addition, we will compare ECochG-based predictions associated with CI electrode scalar position and hearing outcomes to predictions made based on conventional demographic and audiometric data. To facilitate multivariate analysis, we will extract biographical (e.g., age, etiology of hearing loss, duration of deafness) and surgical (e.g., device and electrode type) factors from the electronic medical record.

Statistical Analysis

Randomization

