Block randomization is statistical strategy to prevent unequal numbers of participants from being randomized to one arm vs the other (here, audible signal "on" versus audible signal "off"). For example, using a random number generator set to individually assign 100 participants to one of two groups, there is no assurance that an equal numbers of study participants would end up in the "audible signal on" group, resulting in an unbalanced overall sample, despite randomization of each participant.

Using a block approach, the total sample is divided into smaller blocks and randomization is performed within each block with the rule that the number of allocations is balanced within that block. In our study, although each institution will likely only contribute about 40 participants, we have designed a randomization schedule to allow for 100 participants to be run for each program. This sample of 100 was divided into 50 blocks of two participants; the two participants are randomized ensuring that one goes into the "signal off" group and one goes to the "signal on" group.

Power Analysis

To ensure that our study is appropriately powered to detect a significant difference in the primary outcomes measures, we performed a power analysis with the assistance of a biostatistician. Post-operative CT-based indication of scalar position is treated as a dichotomous variable (i.e., either in the scala tympani or in the scala vestibuli); post-operative hearing outcomes are treated as a continuous variable.

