Scalar Dislocation: Preliminary data indicates that the current state of CI electrode dislocation from the scala tympani to the scala vestibuli is approximately 35% (or, a “successful” scala tympani position is achieved at a rate of 65%). For participants randomized to “ECochG audible signal on,” our expectation, driven by preliminary data, is to decrease the rate of scalar dislocation to approximately 15% (or, a “successful” scala tympani position rate of 85%). Setting the alpha error rate at 2.5%, a total sample size of 192 participants, or 96 participants in each of the two randomization groups, was determined using a Fischer exact test. If we permit a 5% error rate, the total sample size drops to 162 patients (81 randomized to audible signal “on”; 81 randomized to signal “off”). While these numbers of participants are higher than would be possible to achieve at our site alone in an average two-year period, through a coordinated effort to pool multi-center data, it will be easily achievable.

Secondary Planned Analysis

Electrode Type: As detailed above, once a participant is enrolled in the study, the surgeon will select which of two CI electrodes are most appropriate. A secondary analysis comparing scalar position and hearing preservation outcomes will be performed (i.e., four total between-group analyses) between the two electrode groups.

Pediatric Participants: This study will include both adult and pediatric participants. A secondary analysis comparing scalar position and hearing outcomes between adult and pediatric participants will be performed (again, four total between-group analyses).

Regression Analysis: To model the influence of “ECochG on” on the primary outcome measures in the context of participant age group and electrode choice, two regression analyses will be performed – one for the outcome measure of scalar position and one for hearing outcomes.

Hospital Effect Analysis: To determine if there is a meaningful difference in outcome measures across the different participating hospital settings, a secondary analysis will be performed as well.

Safeguarding of Protected Health Information (PHI)

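### The electrode comparison sets surgeon-chosen groups against each other, so as written it mixes the array with pre-operative hearing and institution

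*Protocol*

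**What the plan says.** Three places in the protocol describe how the electrode is assigned, and they agree that the surgeon decides.

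- Outcome Measures: "the surgeon will pre-operatively select the type of CI electrode", after which the patient is randomised.
- Protocol timeline, pre-operative step: "The surgeon makes his or her CI electrode selection between two options", namely SlimJ or MidScala. Pure tone audiometry and the planning CT belong to the same step.
- Secondary Planned Analysis, Electrode Type: "the surgeon will select which of two CI electrodes are most appropriate".

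Randomisation concerns only the audible signal. It uses blocks of two within each institution, and electrode type is not named as a stratum.

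The electrode analysis is a comparison of scalar position and hearing preservation that "will be performed (i.e., four total between-group analyses) between the two electrode groups". No covariate is named and no caution on interpretation is given. Two neighbouring analyses touch on it. The Regression Analysis aims "To model the influence of “ECochG on” on the primary outcome measures in the context of participant age group and electrode choice". The Hospital Effect Analysis is a separate item: "To determine if there is a meaningful difference in outcome measures across the different participating hospital settings". Data Acquisition and Storage also plans to extract age, etiology, duration of deafness and electrode type for multivariate work. That paragraph is about comparing ECochG-based predictions with conventional ones.

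**The concern.** A factor chosen patient by patient because it suits the patient is selected by indication. If surgeons favour one array for ears with better residual hearing, or if an institution leans towards one array, the two electrode groups differ before surgery. The planned contrast then reflects those differences as well as the array.

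The Hospital Effect Analysis has the mirror problem: institutions with different electrode mixes will differ partly for that reason.

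At stake is a reported difference between two arrays, in dislocation or hearing, that could be taken for a property of the device when the design cannot separate it from patient and site selection.

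**Working it through.** **The plan's own figure.** The protocol gives no figure for the electrode comparison. Its sample size concerns the randomised contrast of 35% versus 15% dislocation by Fisher's exact test. Power is not stated. Taking 80% power and a two-sided test, exact power is 80.7% with 96 per arm at alpha 2.5% and 80.2% with 81 per arm at alpha 5%. The smallest sizes reaching 80% are 95 and 81 per arm. The totals of 192 and 162 therefore reproduce to within one patient per arm, and this point does not touch them.

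**What the named regression adjusts for.** Its terms are arm, age group and electrode. According to Outcome Measures the electrode is chosen before randomisation, so arm is balanced across electrode groups in expectation and is not a confounder. Age group is the only named term that can remove confounding of the electrode difference. Pre-operative hearing and institution are not named.

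**Why both matter.** Eligibility requires only a threshold of at most 80 dB HL at 500 Hz, which leaves room for wide variation in baseline hearing. The Objectives define the hearing outcome as post-operative thresholds, which a baseline gap would enter directly. With about 40 participants per institution, 192 / 40 = 4.8, or about five institutions. With so few, local array preference can line up with institution.

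**Illustration for dislocation (assumed inputs).** Suppose there is no electrode effect, a patient or site factor with 15% dislocation if absent and 35% if present, 96 patients per electrode, and prevalences centred on 50%. The false difference is (0.35 − 0.15) × imbalance in prevalence:

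| Imbalance | Rates | False difference | Odds ratio |
|---|---|---|---|
| 10 points | 26% vs 24% | 2 points | 1.11 |
| 20 points | 27% vs 23% | 4 points | 1.24 |
| 30 points | 28% vs 22% | 6 points | 1.38 |
| 40 points | 29% vs 21% | 8 points | 1.54 |

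At the 40-point imbalance a two-sided 5% test rejects about 25% of the time with no electrode effect.

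**Illustration for hearing (assumed inputs).** Let the groups differ by 5 to 15 dB in mean pre-operative threshold, and let post-operative threshold rise 0.6 to 1.0 dB per dB.

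- Raw post-operative threshold: gap × slope, from 5 × 0.6 = 3 dB to 15 × 1.0 = 15 dB.
- Change from baseline: gap × (slope − 1), from 0 dB at slope 1.0 to 15 × (−0.4) = −6 dB, so up to 6 dB in the opposite direction.

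**Room for adjustment.** At the protocol's rates, 96 × 0.35 + 96 × 0.15 = 33.6 + 14.4 = 48 dislocations are expected. Electrode, arm, age group and threshold make four terms. Four indicators for five institutions bring this to eight, and 48 / 8 = 6 events per term. With institution conditioned out or random, 48 / 4 = 12.

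**The count of four.** Two outcomes compared between two electrode groups give two contrasts. Four would arise from on versus off within each electrode for two outcomes, or from electrodes compared within each arm for two outcomes. The first compares randomised arms; the second is confounded in the way described.

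**The case against.** The protocol never calls the electrode contrast unadjusted. Covariates for a secondary comparison are often left to an SAP, and none is shown here. Electrode superiority appears in neither the objective nor the four hypotheses, and the paragraph planning the analysis itself discloses the surgeon's choice. The multivariate work under Data Acquisition and Storage shows that electrode is expected to be analysed alongside patient and audiometric factors. The count of four leaves open that on versus off within each electrode was meant. Adjustment also cannot remove surgeon or anatomical selection.

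Much of this stands, and it limits the point. A reader might infer that the protocol commits to a crude test and will claim a device effect; the text supports neither. A reader might also infer that each institution uses one array only, so that electrode and hospital cannot be separated at all. Nothing in the protocol says so, and it describes surgeons choosing between two arrays.

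What remains is that the protocol names the contrast, names the nearest adjusted model with its terms, and keeps hospital apart from both. The multivariate work serves a different question. The phrase about the two electrode groups favours a direct electrode contrast. If another was intended, the wording needs correcting for that reason.

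**Conclusion.** The point holds as a modest one. Run as written, the electrode comparison is confounded by pre-operative hearing and institution, and the named regression does not cure this. Its size is unknown: the 2 to 8 point and 3 to 15 dB figures rest on inputs that the protocol does not give. The dB range applies only to raw post-operative threshold; for change from baseline it becomes 0 to 6 dB in the opposite direction.

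The analysis is secondary. It would be wrong to infer that the trial's main result is at risk, because the on/off comparison is protected by randomisation and the total of 192 stands.

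**What to change.** In Secondary Planned Analysis:

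- Estimate the electrode difference from one model per outcome containing electrode, arm, age group and pre-operative 500 Hz threshold, with institution as a stratum or random effect. For dislocation use a conditional or penalised logistic model, given about 48 expected events.
- Tabulate electrode by institution, so that sites contributing little or nothing to the comparison are visible.
- State that the electrode result is a non-randomised association that may still reflect surgeon and anatomical selection.
- Keep the Hospital Effect Analysis, with electrode type added as a covariate.
- Explain the count of four between-group analyses. If on versus off within each electrode is meant, say so.

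The cost is analysis wording; the threshold, electrode and institution are already recorded. The downside is a wider interval for the electrode effect and little information from sites that use mostly one array.

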In total, 192 participants will be included in this study. This sample size was determined by a power analysis, detailed below in Statistical Analysis.

Inclusion criteria are:

- Pure-tone audiometry thresholds ≤80 dB HL at 500 Hz
- One year of age and older
- Normal candidacy requirements for cochlear implantation met
- No cochlear abnormality that might prevent full insertion of the CI electrode array
- No additional handicap that would prevent study procedures from being followed

Exclusion criteria are:

- Chronic otitis media
- Malformed cochlea
- Auditory neuropathy spectrum disorder (ANSD)
- Presence of ear tubes
- Prior middle ear surgeries or trauma including disruption of ossicles

At any point in the study, the participants are free to end their involvement without any effect on their clinical care. Because this study does not involve any changes to the CI, its use, or the surgical technique, if a participant were to elect to end involvement in the study, it does not impact their treatment in any way. CI candidates meeting inclusion criteria will be given the opportunity to participate at the time of their regular pre-operative clinic visit or on the day of surgery itself.

Randomization

Interested CI candidates meeting study inclusion criteria will be randomized to one of two treatment arms. Randomization has been accomplished using a “randomized block design” to ensure that equal numbers of participants are included in each “treatment condition.” For each participating institution, an impartially designed randomization schedule has been drawn up with the assistance of a biostatistician. The arm to which participants are randomized will be unknown to the investigators at the time of enrollment and to the participants themselves. By necessity, surgeons themselves will be “unblinded” on the day of surgery. Figure 1 depicts the study’s randomization arms and post-operative outcome measures.

Arm 1: Audible ECochG Response Off

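### Allocation is blocked within institution, but the two regressions for the arm effect name only age group and electrode choice; adding institution would recover a little power at almost no cost (minor)

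*Protocol*

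**What the plan says.** Institution is the stratum of the randomization. The Randomization section under Participants states: "For each participating institution, an impartially designed randomization schedule has been drawn up with the assistance of a biostatistician". The Randomization paragraph under Statistical Analysis adds "This sample of 100 was divided into 50 blocks of two participants", with one member of each pair going to each arm, and expects about 40 participants per institution. The Power Analysis sizes scalar dislocation with an unstratified Fisher test and relies on pooled data from several centers.

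Under Secondary Planned Analysis, the Regression Analysis paragraph describes the model for the arm effect: "on the primary outcome measures in the context of participant age group and electrode choice, two regression analyses will be performed". Institution is not mentioned. It has its own paragraph, the Hospital Effect Analysis, whose aim is "To determine if there is a meaningful difference in outcome measures across the different participating hospital settings". That paragraph does not say that the arm effect will be adjusted for site.

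Data Acquisition and Storage lists further factors for multivariate work, ending "and surgical (e.g., device and electrode type) factors from the electronic medical record". The list is open, but it serves a comparison of ECochG-based with conventional predictions, not the arm regressions.

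**The concern.** The regressions name two covariates that played no part in allocation and leave out the one that did. Blocking within site removes differences between sites from the arm contrast. A model without site does not know this: it keeps the between-site variation in the error term, so the standard error of the arm effect is too large and the test rejects less often than its nominal level. What is at stake is a small amount of power in two secondary analyses, and intervals that are slightly too wide if sites differ.

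**Working it through.** **1. The plan's own figure.** Inputs from the Power Analysis: dislocation 35% against 15%, 96 per arm, alpha 2.5%, Fisher's test. Sidedness and target power are not stated. Exact power is the sum of Bin(x1; 96, 0.35) × Bin(x2; 96, 0.15) over all tables with a two-sided Fisher p ≤ 0.025.
- 96 per arm, alpha 2.5%: 80.7%. The smallest n per arm reaching 80% is 95.
- 81 per arm, alpha 5%: 80.2%. The smallest n per arm is 81.

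Two-sided testing and 80% power thus reproduce both stated totals, 192 and 162. Neither uses site.

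**2. Assumptions for the rest.** Two-sided alpha 2.5% is carried over to both regressions, although the protocol gives it only for scalar dislocation. At about 40 per site there are about 192/40 = 4.8, say five, sites. Between-site variation is not given. The range assumed is a site logit SD of 0 to 1.0 for scalar position and an intraclass correlation (ICC) of 0.02 to 0.10 for hearing.

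**3. Hearing (continuous).** Set the total variance to 1, with share ICC between sites. With arms balanced within site, the arm contrast has variance proportional to 1 − ICC, while a model without site estimates 1. Let s = √(1 − ICC), z = 2.241 (97.5% confidence, two-sided) and d = 2.241 + 0.842 = 3.083, which is 80% power on total variance.
- Without site: power = Φ((d − z)/s), size = 2[1 − Φ(z/s)].
- With site: power = Φ(d/s − z), size 2.5%.

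| ICC | s | Power without site | Power with site | Gain (points) | Size without site |
|---|---|---|---|---|---|
| 0.02 | 0.990 | 80.2% | 80.9% | +0.6 | 2.4% |
| 0.05 | 0.975 | 80.6% | 82.2% | +1.6 | 2.1% |
| 0.10 | 0.949 | 81.3% | 84.3% | +3.1 | 1.8% |

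Gains are taken from unrounded values.

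**4. Scalar position (binary).** Simulation with blocks of two within site and marginal rates held at 35% and 15% (25% in both arms under the null). The logistic likelihood-ratio (LR) models include age group and electrode, with an assumed electrode log odds ratio of 0.7 (20,000 trials). The score test multiplies the variance by n/(n − k) (15,000 trials).

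| Site logit SD | 0 | 0.5 | 0.7 | 1.0 |
|---|---|---|---|---|
| LR without site, size | 2.67% | 2.46% | 2.28% | 1.95% |
| LR without site, power | 85.6% | 85.5% | 86.0% | 86.2% |
| LR with site, size at nominal 2.5% | 2.89% | 2.82% | 2.81% | 2.97% |
| LR with site, power at a true 2.5% size | 84.8% | 85.8% | 86.9% | 88.3% |
| Gain, LR (points) | −0.1* | +0.3 | +0.9 | +2.1 |
| Score with site, size | 2.69% | 2.38% | 2.47% | 2.65% |
| Score, power without / with site | 84.4 / 84.4% | 84.4 / 85.3% | 86.0 / 87.4% | 85.6 / 88.6% |
| Gain, score (points) | 0.0 | +0.9 | +1.4 | +3.0 |

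*At SD 0 the model without site itself runs slightly above 2.5%, so both models are held to 2.5%: 84.87% against 84.77%.

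The simulation error of one power figure is about √(0.86 × 0.14/20,000) = 0.25 points, so the LR gain at SD 0.5 is close to noise. The size of the model without site falls as sites diverge, which is the conservatism described above.

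**The case against.** The best reply is that this is analysis-plan detail. The paragraph states the purpose of a secondary regression in one sentence. It gives no model equation and does not say that its covariates are a closed list, and an analysis plan not shown here may add institution. The hospital analysis is also unspecified and could contain arm and site together. This limits the weight of the point. It does not remove it, because the protocol does choose covariates here and the choice passes over the randomization stratum.

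The size of the gain is open to challenge too, and these challenges stand. Every input on site variation is assumed. The protocol attaches no power or alpha to these regressions. Surgeons choose the electrode, so if that choice differs by site, the planned electrode term already absorbs part of the site variation and the gain is smaller than shown. The repair is also more than a single added word: ordinary LR testing with site terms trades a conservative test for a slightly liberal one.

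A reader might infer that ignoring the stratum invalidates the arm test. It does not: the error moves below the nominal level, not above it. A reader might also infer that the trial is undersized or that the main between-arm comparison must be stratified. The sample size rests on an unstratified Fisher test and reproduces, so neither follows.

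**Conclusion.** The point holds as a minor one. Allocation is stratified by institution, and the regressions as described do not name institution. Across the assumed range, adding site gains between nothing and about 2 to 3 points of power for scalar position, and about 0.6 to 3.1 points for hearing. The upper ends need a site logit SD of 1.0 or an ICC of 0.10, and if sites are alike there is no gain. Type I error is not inflated and N = 192 is unaffected. The protocol's own wish to look for hospital differences shows that such differences are thought possible, but says nothing about their size. It would be wrong to say that site is ignored altogether, or that the protocol rules out adjusting for it.

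**What to change.** Name institution in both regressions and keep age group and electrode choice.
- Hearing: a linear model with site terms.
- Scalar position: a logistic model conditional on (stratified by) site, or a score test with a degrees-of-freedom correction. The figures above cover the score test; the conditional form was not simulated.
- Set in advance a rule for pooling very small sites.

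A plain Cochran-Mantel-Haenszel test by site should not replace the regression, because it would drop the covariates that the regression is there to model.

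The cost is protocol or analysis-plan text, with no added patients, visits or data. The downsides are no gain if sites are alike, an odds ratio that becomes conditional on site, and a size of about 2.8% to 3.0% against 2.5% if an ordinary likelihood-ratio test with site terms is used. Settling this before results are seen also avoids deciding on site adjustment after the hospital comparison is known.
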